10.3 ADVERSE EVENTS AND SERIOUS ADVERSE EVENTS

10.3.1 DEFINITION OF ADVERSE EVENTS (AE)

Adverse event means any untoward medical occurrence associated with the use of an intervention in humans, whether or not considered intervention-related.

10.3.2 DEFINITION OF SERIOUS ADVERSE EVENTS (SAE)

An adverse event (AE) or suspected adverse reaction is considered "serious" if, in the view of either the investigator or sponsor, it results in any of the following outcomes: death, a life-threatening adverse event, a persistent or significant incapacity, or substantial disruption of the ability to conduct normal life functions. Important medical events that may not result in death or be life-threatening may be considered serious when, based upon appropriate medical judgment, they may jeopardize the

participant and may require medical or surgical intervention to prevent one of the outcomes listed in this definition.

10.3.3 CLASSIFICATION OF AN ADVERSE EVENT

10.3.3.1 SEVERITY OF EVENT

For adverse events (Aes) not included in the protocol defined grading system, the following guidelines will be used to describe severity:

- **Mild** – Events require minimal or no treatment and do not interfere with the participant's daily activities.
- **Moderate** – Events result in a low level of inconvenience or concern with the therapeutic measures. Moderate events may cause some interference with functioning.
- **Severe** – Events interrupt a participant's usual daily activity and may require systemic drug therapy or other treatment. Severe events are usually potentially life-threatening or incapacitating. Of note, the term "severe" does not necessarily equate to "serious". For purposes of this study, the following will be considered severe adverse events:
 1. Death
 2. A life threatening experience
 3. Persistent or significant disability/incapacity
 4. Seizure secondary to hypoglycemia
 5. Myocardial infarction that is temporally related to a hypoglycemic (< 70 mg/dL) event
 6. Cardiac dysrhythmia that is temporally related to a hypoglycemic (< 70 mg/dL) event
 7. Reference Glucose Value < 54 mg/dL
 8. Diabetic Ketoacidosis: meeting all criteria: symptoms such as polyuria, polydipsia, nausea, or vomiting, serum ketones > 1.5 mmol/L, either arterial blood pH < 7.30 or venous pH < 7.24, or serum bicarbonate < 15. DKA is suspected as either the primary or a contributing cause for these findings.
 9. Considered severe for any other reason.

Study site personnel must alert Ideal Medical Technologies Inc. or its designee of any severe adverse event (SAE) within 48 hours of investigator awareness of the event via an agreed upon method. Alerts issued via telephone are to be immediately followed with official notification on study-specific SAE forms. See attachment IMT2022-1-A1 for serious adverse event form.

10.3.3.2 RELATIONSHIP TO STUDY INTERVENTION

All adverse events (Aes) must have their relationship to study intervention assessed by the clinician who examines and evaluates the participant based on temporal relationship and his/her clinical judgment. The degree of certainty about causality will be graded using the categories below. In a clinical trial of a medical device, the medical device under study must always be suspect.

- **Related** – The AE is known to occur with the study intervention, there is a reasonable possibility that the study intervention caused the AE, or there is a temporal relationship between the study intervention and event. Reasonable possibility means that there is evidence to suggest a causal relationship between the study intervention and the AE.
- **Not Related** – There is not a reasonable possibility that the administration of the study intervention caused the event, there is no temporal relationship between the study intervention and event onset, or an alternate etiology has been established.

10.3.3.3 EXPECTEDNESS

The principal investigator will be responsible for determining whether an adverse event (AE) is expected or unexpected. An AE will be considered unexpected if the nature, severity, or frequency of the event is not consistent with the risk information previously described for the study intervention.

10.3.4 TIME PERIOD AND FREQUENCY FOR EVENT ASSESSMENT AND FOLLOW-UP

The occurrence of an adverse event (AE) or severe adverse event (SAE) may come to the attention of study personnel during study visits or upon review by a study monitor.

All Aes including local and systemic reactions not meeting the criteria for SAEs will be captured on the appropriate case report CRF. Information to be collected includes event description, time of onset, clinician's assessment of severity, relationship to medical device under study (assessed only by those

DEMONSTRATION OF AN ARTIFICIAL INTELLIGENCE BASED CLOSED LOOP GLUCOSE CONTROL SYSTEM AS A THERAPEUTIC MODALITY IN TYPE 1 AND TYPE 2 DIABETIC PATIENTS

Protocol IMT 2022-1

CONFIDENTIAL

Version1.0.7

22 August 2022

with the training and authority to make a diagnosis), and time of resolution/stabilization of the event. All Aes occurring while on study must be documented appropriately regardless of relationship. All Aes will be followed to adequate resolution.

Any medical condition that is present at the time that the participant is screened will be considered as baseline and not reported as an AE. However, if the study participant's condition deteriorates at any time during the study, it will be recorded as an AE.

Changes in the severity of an AE will be documented to allow an assessment of the duration of the event at each level of severity to be performed. Aes characterized as intermittent require documentation of onset and duration of each episode.

The Principal Investigator or his designee will record all reportable events with start dates occurring any time after informed consent is obtained until 1 (for non-serious Aes) or 3 days (for SAEs) after the last day of study participation. At each study visit, the investigator will inquire about the occurrence of AE/SAEs since the last visit. Events will be followed for outcome information until resolution or stabilization.

Unsolicited adverse events are not applicable to this study.

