11.4.4 SAFETY ANALYSES

For the safety primary endpoint of percent time in range < 70 mg/dL, the calculation is as follows:

(# of glucose values in range < 70 mg/dL/total number of all glucose values) * 100

This result will be presented as median and interquartile range (25-75).

Each AE or SAE will be independently reported as percent of patients experiencing the event. SAE's that require stopping the study prematurely will be separately reported in a table. If the principal investigator feels the AE or SAE's are secondary to the intervention this will be reported in the final study summary. Any rescue medicine that is used per 8.5.1 will be separately reported as percent of subjects requiring rescue medicine.

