| | 
Both type 1 and type 2 diabetic subjects will consume a lunch consisting of 60 grams of carbohydrates beginning at 1200 hours on day 2.
 
The study nurse will check Reference Glucose Values every 30 minutes with the Nova StatStrip Hospital Glucose Meter System – Times 29, 29.5, 30, 30.5, 31, 31.5, and 32 hours, etc., until the subjects Reference Glucose Values are in the range of 80-250 mg/dL for a period of at least two hours after the completion of the closed loop glucose control session, and the most recent glucose rate of change is less than \pm 2 mg/dL/min.
 
If the subject is removed from the study early due to the presence of hypoglycemia (e.g., < 54 mg/dL or < 70 mg/dL with neuroglycopenic symptoms) or for any other reason, they will have ongoing monitoring in the CRC until they have had glucose values in the range of 80-250 mg/dL for a period of at least two hours, and until their most recent glucose rate of change is less than \pm 2 mg/dL/min. In the event the subject is removed from the study early, any short or long acting insulin dosing needed from the time the subject is removed from the study until the time the subject is discharged from the CRC, will be per the orders of the study's principal investigators ([name] or [name]).
 
If the subjects CGM or Reference Glucose Values are less than 70 mg/dL at the time they are removed from the study, they will have Reference Glucose Values measured every 10 minutes until such time as their glucose values are greater than 70 mg/dL. If the subject develops signs of diabetic ketoacidosis (e.g., Reference Glucose Value > 240 mg/dL and blood ketones > 1 mmol/L), they will have a basic metabolic panel, venous pH, and beta hydroxybutyrate drawn. If the subject develops diabetic ketoacidosis, they will be stabilized and have ongoing care per the usual routine of Emory Healthcare.
 |
| 21. | 
Intravenous Catheter Removal:
 
Remove both IV catheters once the subjects Reference Glucose Value is in the range of 80-250 mg/dL for a period of at least two hours after the completion of the closed loop glucose control session, and when the most recent glucose rate of change is less than \pm 2 mg/dL/min. This criterion will not be met prior to time 32 hours (\sim 1500 hours of 2nd day in the CRC). The subject may be discharged from the CRC unit once this criterion has been met.
 |

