| 22. | 
Discharge Criteria
 
The subjects Reference Glucose Value must be between 80-250 mg/dL for a period of 2 hours before discharge, and their most recent glucose rate of change must be less than \pm 2 mg/dL/min. For subjects who have been placed back on their usual continuous subcutaneous insulin infusion pump, they may be discharged once their Reference Glucose Value is between 80-250 mg/dL for a period of 2 hours, and their most recent glucose rate of change must be less than \pm 2 mg/dL/min.
 |

DEMONSTRATION OF AN ARTIFICIAL INTELLIGENCE BASED CLOSED LOOP GLUCOSE CONTROL SYSTEM AS A THERAPEUTIC MODALITY IN TYPE 1 AND TYPE 2 DIABETIC PATIENTS

Protocol IMT 2022-1

CONFIDENTIAL

Version1.0.7

22 August 2022

| | |
|------------|--|
| | 
All subjects must be observed for a minimum of 3 hours after the conclusion of the closed loop glucose control session and for at least 60 minutes after their most recent subcutaneous insulin injection (subjects on MDI insulin therapy), before being discharged from the CRC.
 
End of Study Reference Glucose Value, BG: _____ mg/dL, Time: _____ (24 hour clock)
 |
| 23. | 
After the subjects have been discharged from the CRC, they will be instructed to check their blood glucose levels at home using their blood glucose meter at the following times:
 
1. On arrival at home.2. Before dinner.3. At 9 P.M.4. On awakening the next morning. 
Subject to call study coordinator with concerns they have about their glucose levels or any other issue.
 |

Attachment 1

Serious Adverse Event Report Form

IMT2022-1-A1

Serious Adverse Event

An adverse event is any untoward medical event associated with use of a drug or drug delivery system in humans, whether or not it is considered related to a drug or drug delivery system. For purposes of this study, a Serious Adverse Event (SAE) is any adverse event from this study that results in one of the following outcomes:

- Death
- A life threatening experience
- Persistent or significant disability/incapacity
- Seizure secondary to hypoglycemia
- Myocardial infarction that is temporally related to a hypoglycemic (<70 mg/dL) event
- Cardiac dysrhythmia that is temporally related to a hypoglycemic (<70 mg/dL) event
- Any other complication related to hypoglycemia
- Reference Glucose Value less than 54 mg/dL
- Considered significant for any other reason

Serious Adverse Event (SAE) Report Form

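### The adverse event window runs 1 day (3 days if serious) past participation, but no staff-initiated contact is scheduled after discharge, so events in it may be missed

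*Combined protocol and SAP*

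**What the plan says.** Section 10.3.4 sets the window: reportable events are recorded if they start "any time after informed consent is obtained until 1 (for non-serious Aes) or 3 days (for SAEs) after the last day of study participation". It says that events "may come to the attention of study personnel during study visits or upon review by a study monitor", and it places active enquiry at visits: "At each study visit, the investigator will inquire about the occurrence of AE/SAEs since the last visit". It also states: "Unsolicited adverse events are not applicable to this study".

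The last visit is Visit 3. On the condition for removing catheters and discharging the subject, Protocol 2 item 21 says: "This criterion will not be met prior to time 32 hours", which it places at about 1500 on the second day.

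Protocol 2 item 23 covers the time after discharge. Subjects are told that "they will be instructed to check their blood glucose levels at home using their blood glucose meter at the following times": on arrival home, before dinner, at 9 PM and on waking the next morning. Contact is left to them: "Subject to call study coordinator with concerns they have about their glucose levels or any other issue".

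Section 9.3 rules out long-term follow-up, with an exception for recording and monitoring adverse events or unanticipated problems as required. Section 9.4 (lost to follow-up) is marked not applicable. The output affected is in section 11.4.4: "Each AE or SAE will be independently reported as percent of patients experiencing the event".

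**The concern.** The protocol creates a duty to record events over a period in which nobody is scheduled to ask about them. When a subject has not been asked and does not call, the record looks the same as that of a subject who had no event.

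The period is not an idle one. Protocol 2 item 20 moves subjects from the device's intravenous control back to subcutaneous insulin or their own pump just before or after the session ends, and item 23 itself asks for glucose checks through the next morning. Scheduled inspection of the sensor sites stops at time 32 hours (item 13). A low that the subject treats at home, or a sensor-site or catheter-site problem that appears the next day, would fall in the window. Under section 10.3.3.2 a temporal relationship is enough to class an event as related, so such events could count against the device.

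At stake are the AE and SAE percentages of an early feasibility study. The cumulative data that the Independent Safety Monitor weighs (section 12.1.6) and the rule that any unanticipated adverse device effect ends the study (section 9.2) also depend on such events being found.

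**Working it through.** The plan states no calculated figure on this point, so there is none to reproduce. The check compares the window with the scheduled enquiries and then counts.

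**Inputs**
- Window after the last day of participation: 1 day (non-serious) or 3 days (SAE), section 10.3.4.
- Earliest discharge: time 32 hours, about 1500 on day 2, Protocol 2 item 21.
- Home readings: 4 per subject, Protocol 2 item 23.
- Subjects: 8, section 11.2. All who begin closed loop control are analysed, section 11.3.

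**Length of the window without a scheduled enquiry.** The text does not say whether days are elapsed or calendar days, so both are shown, from discharge at 1500 on day 2. There are 24 − 15 = 9 hours left on day 2.

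| Event type | Elapsed days | Calendar days |
|---|---|---|
| Non-serious AE | 1 × 24 = 24 h, to 1500 on day 3 | 9 + 24 = 33 h, to the end of day 3 |
| SAE | 3 × 24 = 72 h, to 1500 on day 5 | 9 + 72 = 81 h, to the end of day 5 |

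**Scheduled enquiries in that time.** Section 10.3.4 ties enquiry to visits, and Visit 3 is the last. In the Schedule of Activities (section 1.3) the final column has lost its heading in the text available here. It marks study intervention and vital signs as well as AE review, which fits the in-centre recovery period and not a later contact. Scheduled staff-initiated contacts after discharge: 0 for each of 8 subjects.

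**Home readings.** 8 × 4 = 32 readings are requested. All fall inside the 1-day window if the subject wakes before 1500 on day 3. The protocol states no step to record, return or transcribe them.

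**Effect on the reported percentage.** One subject is 1/8 = 12.5 percentage points. An event seen in no subject is reported as 0/8 = 0%; if one subject's event was missed, the true figure is 12.5%.

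**Classification of a home reading.** Section 10.3.3.1 and Attachment 1 write the <54 mg/dL criterion for a Reference Glucose Value, which section 4.1 defines as a bedside result on the hospital meter. A home-meter value below 54 mg/dL does not meet that criterion as written, even if the subject reports it. It could enter only through the general categories in those lists.

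**The case against.** A reader might infer that there is no contact at all after discharge, that visit enquiry is the only stated means of finding events, that the home readings are never collected, and that post-discharge events go uncounted. The documents do not support that reading:

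- Protocol 2 item 23 gives subjects a route to the coordinator for glucose concerns or anything else.
- Section 9.3 permits follow-up as required for adverse events.
- Section 10.3.4 names monitor review as a second way of finding events. Section 12.1.7 requires 100% data verification after each session, and section 12.1.3 gives monitors access to medical records.
- The duty to record reportable events in the window covers an event that is phoned in. The sentence on unsolicited events sits badly with that duty but does not cancel it.
- Silence on the home readings is not a plan to discard them. The case report forms, consent form and monitoring plan are separate documents not seen here and might provide for a diary or a call, though the protocol refers to neither.

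The importance also has limits. The synopsis sets the time frame of the primary and secondary endpoints as start to end of controller use, so none of them changes. The AE and SAE percentages are descriptive, with no test or threshold. The 12.5 points is the weight of one subject and does not estimate how many events would be missed.

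All of this stands, but none of it is a scheduled enquiry. The section 9.3 exception helps only once someone knows of an event. Record review can find a documented hospital contact but not a low treated at home. The call route works only if the subject thinks the matter worth a call.

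**Conclusion.** The point holds in this form: no scheduled staff-initiated contact covers the 1-day and 3-day window, capture depends on subject-initiated calls or record review, and the protocol states no collection step for the home readings. Post-discharge events may be missed; it cannot be said that they will be.

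The uncovered time is 24 to 33 hours for non-serious events and 72 to 81 hours for SAEs, in all 8 subjects. Each missed subject lowers a reported percentage by 12.5 points. The effect is confined to the AE and SAE summaries and the safety oversight that draws on them.

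The conclusion assumes discharge at the earliest permitted time, 8 analysed subjects, and no contact or diary specified in the separate documents. The change should be made: it costs little, and it gives the protocol a planned means of filling a window that it has set for itself.

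**What to change.** 1. Add two coordinator telephone contacts to the Schedule of Activities, and state whether the windows are counted in elapsed or calendar days.
   - First call, at or after the close of the 1-day window: record the four home readings and ask about all AEs and SAEs. On the elapsed count this is no earlier than 1500 on day 3 for a subject discharged at 1500 on day 2, and on the calendar count it is after the end of day 3. A call on the morning after discharge would be too early.
   - Second call, at or after the close of the 3-day window: ask about SAEs, and about any non-serious AE that began within the 1-day window.
2. Enter both calls on the case report form, and report how many subjects were reached at each, so that a subject not asked is not read as event-free.
3. Delete the sentence on unsolicited events, or reconcile it with item 23, so that phoned-in events count.
4. State how a home-meter value is reported and classified, given that the <54 mg/dL criterion is written for a Reference Glucose Value.

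Cost: 8 × 2 = 16 short calls by the existing coordinator, one Schedule of Activities column and one form page, with 32 readings to enter. The reported AE rate may become slightly less favourable.

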10.3.5 ADVERSE EVENT REPORTING

Adverse events will be reported by the Principal Investigator to the Institutional Review Board and study sponsor if in the opinion of the Principal Investigator the adverse event was caused by or related to use of the medical device under study.

10.3.6 SERIOUS ADVERSE EVENT REPORTING

If during the course of this study a serious adverse event occurs, the Principal Investigator shall complete an Unanticipated Adverse Device Effect Form and submit to the study sponsor and to the reviewing Institutional Review Board (IRB) as soon as possible, but in no event later than 10 working days after the investigator first learns of the effect. The study sponsor is responsible for conducting an evaluation of an unanticipated adverse device effect and shall report the results of such evaluation to the Food and Drug Administration (FDA), the IRB and the Principal Investigator within 10 working days after the sponsor first receives notice of the effect. Thereafter, the sponsor shall submit such additional reports concerning the effect as FDA requests.

10.3.7 REPORTING EVENTS TO PARTICIPANTS

Adverse Events and Serious Adverse Events will be reported to the participants of this study if in the opinion of the Principal Investigator they are related to the medical device under study.

10.3.8 EVENTS OF SPECIAL INTEREST

Any medical device malfunction that either impedes or prevents the carrying out of this study will be reported to the sponsor, IRB, and regulatory agencies.

10.3.9 REPORTING OF PREGNANCY

If during the course of this study, a subject has signed an informed consent and is found to be pregnant prior to the treatment phase of the study, this subject will be informed of the positive pregnancy test and the fact that this excluded them from the treatment phase of the study.

10.4 UNANTICIPATED PROBLEMS

10.4.1 DEFINITION OF UNANTICIPATED PROBLEMS (UP)

Unanticipated problems will be considered those that involve risks to participants or others to include, in general, any incident, experience, or outcome that meets all the following criteria:

- Unexpected in terms of nature, severity, or frequency given (a) the research procedures that are described in the protocol-related documents, such as the Institutional Review Board (IRB)-approved research protocol and informed consent document; and (b) the characteristics of the participant population being studied;
- Related or possibly related to participation in the research (“possibly related” means there is a reasonable possibility that the incident, experience, or outcome may have been caused by the procedures involved in the research); and
- Suggests that the research places participants or others at a greater risk of harm (including physical, psychological, economic, or social harm) than was previously known or recognized.

This definition could include an unanticipated adverse device effect, any serious adverse effect on health or safety or any life-threatening problem or death caused by, or associated with, a device, if that effect, problem, or death was not previously identified in nature, severity, or degree of incidence in the investigational plan or application (including a supplementary plan or application), or any other unanticipated serious problem associated with a device that relates to the rights, safety, or welfare of subjects.

